Title of Project:

Effectiveness of Ankle-7 orthosis vs AFO orthosis on gait performance in diplegic cerebral palsied children.

Protocol ID: UDGEE_2012_OTTObock

BACKGROUND (knowledge already available on the effectiveness of the intervention)

The hypertonic muscle is a major cause of disability in children with cerebral palsy (PCI). A typical clinical manifestation of PCI is represented by spastic diplegia, affecting about 40% of this population. The movement disorder in children with CP results from the involvement of structures belonging to the central nervous system (top-down components) associated with variable involvement of structures belonging to the musculoskeletal system (bottom-up components). Both top-down and bottom-up components may provide clinical variables, the direct consequence of this phenomenon is that children with diplegia and PCI express more than one pattern of walking, different from the physiological one, each of which is characterized by more or less marked involvement of different muscles of the lower limbs.

The orthoses are frequently used to improve the ability of children with CP although, to date, the level of scientific evidence in support of their use is still limited. Improving the way through the most appropriate use of the orthoses requires the clinician with an understanding of spontaneous motor pattern and strategies adopted by the child during walking. To make a successful prescription, pathophysiology and pathological elements in the biomechanics of gait kinematics should be carefully considered and put into relation with the biomechanical characteristics of orthosis you have.

In recent years, we proposed a classification of spastic diplegia in childhood that can distinguish four different forms, according to the pattern of walking. (Ferrari et al, 2005) The second of these forms affects approximately 35% of children with diplegia and PCI and is characterized by knee flexing in mid-stance and sagittal swinging of pelvis. The classification of the forms of diplegia has already been tested for its inter-operator reliability (Ferrari et al, 2008) and the criterion validity (Ferrari et al, 2008). In choosing the most suitable orthosis, the clinician should try to integrate its objectives, in terms of improved kinematics and kinetics of the way, with the priority functional needs expressed by the child and the family, taking into account technical and economic constraints. The Ankle Foot Orthosis (AFO) is the most commonly used orthosis in diplegic PCI children. However, recently it has been proposed an orthosis of new design that contains a carbon fiber component whose purpose is to store and return energy during the succession of phases of the gait cycle. The effects of this orthosis in children with diplegia and PCI have never been studied nor compared with the effects of AFO in this population.

OBJECTIVES OF THE STUDY

- What the study aims to demonstrate:

The aim of this work is to verify the superiority of the ankle-7 orthosis compared to the more widespread AFO, to improve the functionality and walking function of children with spastic diplegia and PCI. The effectiveness of the orthosis will be evaluated objectively using gait analysis and the use of the Goal Attainment Scale.

- What the study helps to add to current knowledge:

To date, there are no studies demonstrating the efficacy of ankle-7 orthosis on the walking function in this patient population. Furthermore, the level of scientific evidence to support the use of orthoses in spastic diplegia resulting from PCI, to date, is still limited. However, the use of orthoses in this population is widespread.

STUDY DESIGN

Monocentric	✓	Complex Structure of Rehabilitation of Severe Developmental Disabilities - ASMN of Reggio Emilia (Italy)
Sponsored Independent	✓	Proposer: UOC Rehabilitation of severe developmental disabilities, Department of Obstetrics - Gynecology - Pediatric ASMN Reggio Emilia The study is funded by the Company OttoBock The data are owned by the applicant and the structure of its affiliation

Study population

Children with PCI belonging to the 2nd form of spastic diplegia, afferent to the 3rd level for Severe Developmental Disabilities at Hospital Santa Maria Nuova, Reggio Emilia, aged between 6 and 18 years. To be included in the study, children must have a clinical and instrumental diagnosis of PCI, consisting of a complete medical history and results of magnetic resonance imaging.

According to our hypothesis, the use of the ANKLE-7 orthosis will improve the power generated by the ankle joint during the push off. The data in our possession allows us to hypothesize that a minimum of 22 cases must be selected to meet inclusion and exclusion criteria for a study power of 80% with a Type I error of 5%. However, this calculation is based on very few cases followed very heterogeneous amongst themselves. For this reason, we intend to proceed to recruitment in two phases. In the first phase of "pilot" study, 5 children will be selected to meet the eligibility criteria for the study in order to more accurately identify the expected gain with the use of ANKLE-7 orthosis compared to the most common AFO articulated, on the outcome measure we consider to be our main and secondary measures. In the second phase, after verification of the power and feasibility of the study, we will proceed to the completion of the sample.

N° of people involved in the center: 22

first phase 5, second phase to be verified, according to our initial hypothesis 17

Duration of the study: from May 2012 to May 2014.

Criteria for inclusion

- Clinical indication to the use of orthoses to improve the walking function confirmed by instrumental parameters obtained from analysis of the path (dynamic electromyography, optoelectronic stereophotogrammetry analysis);
- Patients who already have AFO orthoses (or ankle-7) that need to be renewed;
- Patients with new clinical indication to the use of orthoses but not yet in possession of the same;
- Informed consent from parents / guardians of the child.

Criteria for exclusion

- Cognitive disabilities that may affect the child's participation in the activities related to this study, in the opinion of the investigators;
- Lower limbs sensory disability that may affect any beneficial effects of the use of the orthoses, in the opinion of the investigators;
- Other diseases associated or not associated with PCI that, according to investigators, could affect the child's participation in the activities related to this study (eg: drug-resistant epilepsy);
- Administration of antispasmodic drugs in the last 6 months;
- Functional surgery of the lower limbs in the last 6 months;
- Indication for surgical treatment to be carried out within 6 months after the date of inclusion in the study.

Outcome measures:

1_ power generated from the right and left ankle joints in the boost phase, measured by instrumental gait analysis

2_level of the knee joint kinematics: average extension in degrees of the right and left knees during initial contact, loading response and mid-stance calculated on a minimum of three walks or 15 steps, measured by instrumental gait analysis;

3_ stride length sn and dx, measured by instrumental gait analysis;

4_ walking speed measured by instrumental gait analysis;

5_ energy expressed during the walking;

7_ preference of use of AFO or Ankle_7, determined from the diary;

8_ clinical evaluation of the walking function, through the video-recording of the same and the Visual Gait Assessment Scale (OGS). (Boyd R, Graham HK. 1999; Eur J Neurol 6: S23-S35)

An independent observer, with at least ten years of clinical experience in the field of PCI, blinded to the allocation of children in the two groups, observe the videotapes of each child while walking using O_1 or O_2 covered with gaiters and will give an assessment of clinical improvement or worsening of the second situation compared to the first. For this purpose we will use the OGS, a validated observational assessment scale of gait.

An independent observer, with at least ten years of clinical experience in the field of PCI, blinded to the allocation of children in the two groups, observe the graphical reports of instrumental gait analysis of every child while using O_1 or O_2 and will give an assessment of clinical improvement or worsening of the second situation compared to the first.

Proposed intervention

The study is experimental and prospective, with a cross-over design.

The project is divided into the following phases:

T0 – at the beginning of the study children included will be subject to the following procedures and assessments:

- 1) demographic and anthropometric data collection;
- 2) randomization by concealed allocation to one of the following two groups:

- AFO - Ankle_7 group

- Ankle-7 – AFO group

Both, AFO and ankle-7, will be tailored to the patient

The two groups are distinguished by the order of the assignment of the two orthoses, respectively defined as the first assignment orthosis (O_1) and second assignment orthosis (O_2). The first group will use the hinged AFO orthosis (**tailor-made with range of motion of about 20 ° (-5 - + 15) from the indifferent position with ankle joint at 90 °**) as a first assignment and then the orthoses Ankle_7, while the second group will use the two orthoses according to the reverse order. The two will be used with the same orthotic footwear, with the exception of the cases where it will be necessary to change it due to accretion.

3) collection of the measures necessary for making the two orthotic devices at OttoBock of Reggio Emilia

4) training in the use of the orthoses according to a standardized protocol;

5) try on the patient's in-process first assignment orthoses (O_1) and subsequent delivery of them (see Annex A);

Subsequently, the patient will use O_1 for a period of 4-6 weeks.

T1 - patients will receive the following procedures and assessments:

1. try on the patient's in-process second assignment orthoses (O_2)
2. instrumental gait analysis and video recording of the walking while using O_1 (covered by elastic gaiters);
3. withdrawal of O_1
4. delivery of O_2 to the patient

Subsequently, the patient will use O_2 for a period of 4-6 weeks.

T2 - patients will undergo the following procedures and evaluations:

1. instrumental gait analysis and video recording of the walking while using O_2 (covered by elastic gaiters);
2. return of O_1 to the patient;
3. Delivery of the diaries and directions for completing and mailing back them at the end of the

follow-up period;

T3 - three months follow-up to detect the preference of use of AFO or Ankle-7 (by the child/parent)

Hypothesis	Superiority
Randomization	YES Concealed allocation
Blinding	Single blind (assessor)
Study monitoring	Promoter

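### Does naming both the right and the left ankle in outcome 1 break the 5% error rate behind the 22 children?

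*Protocol*

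**What the plan says.** Under Study population, the Protocol's hypothesis is that "the use of the ANKLE-7 orthosis will improve the power generated by the ankle joint during the push off". The ankle is in the singular and no side is named. The sample size follows directly: "a minimum of 22 cases must be selected to meet inclusion and exclusion criteria", and this is "for a study power of 80% with a Type I error of 5" per cent. The same section counts people, not limbs: "N° of people involved in the center: 22".

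Under Outcome measures, item 1 is "power generated from the right and left ankle joints in the boost phase, measured by instrumental gait analysis". Item 3 is also two-sided: "stride length sn and dx, measured by instrumental gait analysis". Item 2 is worded as an average, "average extension in degrees of the right and left knees during initial contact, loading response and mid-stance", taken over at least three walks or 15 steps.

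The Protocol names no statistical test. It does not say whether the two ankles are averaged, tested separately, both required, or modelled as two limbs within a child. Study population mentions main and secondary measures, but the outcome list carries no such labels.

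**The concern.** One hypothesis with one 5% error rate needs one number per child per orthosis. Item 1, read literally, gives two. If each side were tested at 5% and a positive result on either were called superiority, the trial would have two chances to succeed. If each limb were counted as a case, 22 children would become 44 observations whose correlation is ignored. Either way, the superiority claim would carry more than the stated 5%. The wording of item 2 as an average makes it look as if the sides in item 1 were kept apart on purpose. Keeping them apart could also waste precision that a bilateral measurement provides at no extra cost.

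**Working it through.** **Inputs.** From the Protocol: n = 22 children, 5% Type I error, 80% power, a two-sequence cross-over. Not given: effect size, SD, whether the test is one- or two-sided, and the correlation ρ between the left and right within-child device differences. I assume a two-sided test and equal variances on the two sides, ignore period effects, and let ρ run from 0 to 1.

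**The Protocol's own figure.** The 22 cannot be reproduced without an effect size, so it is solved backwards. By the normal approximation, d = (1.960 + 0.842)/√22 = 2.802/4.690 = 0.60. The paired t-test with 21 degrees of freedom gives 0.63, and the cross-over t-test with 20 degrees of freedom also gives 0.63. Nothing in this shows whether the 22 was worked out for one ankle or for a per-child summary.

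**Type I error by way of handling the two sides.** For two independent tests, 1 − 0.95² = 9.75%. For naive pooling, the true variance of the mean of 44 limbs is σ²(1 + ρ)/44, while the analysis uses σ²/44. The error is therefore about 2[1 − Φ(1.96/√(1 + ρ))], which is 11.0% at ρ = 0.5 and 15.5% at ρ = 0.9. Simulation (100,000 trials of 22 children for each ρ) gives:

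| ρ | Either side at 5% | 44 limbs as independent | Mean per child | Both sides required | Either side at 2.5% |
|---|---|---|---|---|---|
| 0 | 9.7% | 5.0% | 4.9% | 0.1% | 4.8% |
| 0.3 | 9.4% | 8.4% | 5.0% | 0.4% | 4.8% |
| 0.5 | 9.0% | 11.0% | 5.0% | 0.8% | 4.6% |
| 0.7 | 8.4% | 13.6% | 5.0% | 1.6% | 4.3% |
| 0.9 | 7.1% | 16.1% | 4.9% | 2.8% | 3.6% |
| 1 | 5.0% | 17.2% | 5.0% | 5.0% | 2.5% |

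Only the first two approaches inflate the error, and each is harmless at one end of the range of ρ. The other three hold 5%, apart from simulation noise of a few hundredths of a percentage point.

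**Precision.** If the 22 was computed for one limb and both sides have equal effects and variances, averaging raises the standardised effect to 0.626/√((1 + ρ)/2). Power is then 90% at ρ = 0.5, 86% at 0.7 and 82% at 0.9. If the 22 already rests on a per-child value, the gain is nil. The Protocol does not say which applies, so no gain can be claimed from it.

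**Set against the text.** The singular ankle in the hypothesis and the count of 22 people fit one value per child. An either-side success rule and a count of 44 limbs appear nowhere. The contrast with item 2 is weak, because its average may run over steps rather than over sides.

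**The case for a change.** The strongest reply is that the definition of the powered outcome belongs in the protocol, and that here it has consequences. Five pilot children are used to refine the expected gain and to verify the power before recruitment is completed. The gain and its SD depend on whether the variable is the right ankle, the left ankle or the mean, so an undefined outcome leaves room to choose after pilot data have been seen. The permissible rules also differ in cost. At the effect implied by 22 children, splitting the 5% between sides lowers power per side from 80% to about 70% and raises the number needed to about 27. Requiring both sides gives an error as low as 0.1%.

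It stands that the Protocol gives no derivation rule and that the rule should be settled before pilot results are examined. That is ordinary content for a statistical analysis plan, which may exist and was not available. The silence does not show that a side will be chosen late, nor that an inflating analysis is intended. The missing labels for main and secondary outcomes add little, since the hypothesis and the power statement both point to ankle push-off power, which is listed first.

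**Conclusion.** The concern does not call for a change. Item 1 states what is measured; it does not state an analysis that breaks the 5% error. The inflated rates, about 7-10% for unadjusted either-side testing (ρ from 0 to 0.9) and about 8-16% for limbs treated as independent (ρ from 0.3 to 0.9), belong to analyses the Protocol does not adopt. They rest on an assumed correlation, equal variances and no period effect. Averaging the two sides within each child is the obvious reading, agrees with the hypothesis and the count of children, holds 4.9-5.0% throughout, and needs no more than 22. What remains is a gap that an analyst would fill sensibly: how two ankle readings become one value per child. A sound analysis is fully available under the text as it stands.

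### Both blinded readings ask whether the second record is better than the first, which cues visit order and can cost a little power on a better/worse answer

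*Protocol*

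**What the plan says.** Protocol, Outcome measures, describes two readings by an independent observer who is "blinded to the allocation of children in the two groups".

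- Video reading (with outcome 8): the observer is to "observe the videotapes of each child while walking using O_1 or O_2 covered with gaiters". The scale is named: "For this purpose we will use the OGS, a validated observational assessment scale of gait".
- Graphical-report reading: the observer is to "observe the graphical reports of instrumental gait analysis of every child while using O_1 or O_2". No scale is named, and the text does not say whether the answer is graded.

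Both paragraphs end with the same rating rule: the observer "will give an assessment of clinical improvement or worsening of the second situation compared to the first".

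Protocol, Proposed intervention, fixes what first and second mean. The two sequence groups differ in the order of the orthoses, "respectively defined as the first assignment orthosis (O_1) and second assignment orthosis (O_2". The T1 list has "instrumental gait analysis and video recording of the walking while using O_1 (covered by elastic gaiters", and the T2 list has the same for the other orthosis: "instrumental gait analysis and video recording of the walking while using O_2 (covered by elastic gaiters". The design is a cross-over with assessor blinding.

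**The concern.** On its natural reading, the rating question tells the observer which of a child's two records is the later one. Blinding to sequence group, and the gaiters on the videos, hide which device is O_1. They do not hide which record is O_1, and nothing in the protocol codes the records or shuffles their order.

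An observer who expects children to improve over the study may lean towards calling the later record better. In this cross-over the later record is Ankle-7 in one group and AFO in the other, so the lean is a period effect and not a device effect. The stake is therefore not a false claim for a device. It is possible loss of power: if the answer is only better or worse, a lean pushes both groups towards one end of the scale and leaves less room for a device difference to show.

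This belongs to the protocol because the question is fixed when the records are read. A later analysis can adjust the recorded answers, but it cannot change the question that was asked.

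**Working it through.** **What the protocol supplies.** It gives a total of 22 (Study population), two sequences, and the direction of the comparison. It gives no figure for the observer readings, so there is none to reproduce. The 22 relates to ankle push-off power, and no effect size or SD is stated. Taken as a paired comparison at two-sided 5% and 80% power, it implies a standardised within-child difference of (1.960 + 0.842)/√22 ≈ 0.60. That has no bearing on this point.

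**Assumptions, none from the protocol.** 11 children per sequence. An answer of better or worse. A share *p* of children in whom Ankle-7 would be rated better with no order tendency (0.80; range 0.75 to 0.85). A share *s* of second records rated better when the devices do not differ.

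**Model.** The tendency is a shift on the logit scale. The chance that the second record is rated better is

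- AFO then Ankle-7: expit(logit *s* + logit *p*)
- Ankle-7 then AFO: expit(logit *s* − logit *p*)

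Example at *s* = 0.65, *p* = 0.80: logit *s* = 0.619 and logit *p* = 1.386, giving expit(2.005) = 0.881 and expit(−0.767) = 0.317.

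**Test.** Fisher's exact test of the answer between sequences, two-sided 5%, fully enumerated. A tendency common to both sequences cancels in this comparison, so it is a period-adjusted test. The last column repeats it with a probit shift, Φ(Φ⁻¹(*s*) ± Φ⁻¹(*p*)).

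| *s* | Second rated better, AFO first | Second rated better, Ankle-7 first | Power, logit | Power, probit |
|---|---|---|---|---|
| 50% | 0.800 | 0.200 | 73.4% | 73.4% |
| 55% | 0.830 | 0.234 | 72.8% | 72.9% |
| 60% | 0.857 | 0.273 | 70.9% | 71.2% |
| 65% | 0.881 | 0.317 | 67.8% | 68.6% |
| 80% | 0.941 | 0.500 | 48.2% | 52.7% |

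The loss is 5 to 6 points at 65% (73.4 − 68.6 and 73.4 − 67.8) and about 21 to 25 points at 80% (73.4 − 52.7 and 73.4 − 48.2).

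**Sensitivity.**

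- *p* = 0.75 (logit, *s* = 50/55/60/65%): 52/51/49/46%. At *p* = 0.85: 90/90/89/87%.
- Mid-p version of the test (probit, *p* = 0.80): 87% with no tendency, 85% at *s* = 60%, 71% at 80%.
- A 13:9 split (probit, *p* = 0.80): 75.7% with no tendency, 76.1% at *s* = 60% (no loss), 60.0% at 80%.

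**No device difference.** At 11:11 the expected share favouring Ankle-7 stays at 50% whatever the tendency, and Fisher's test rejects at most 1.7% of the time. At an assumed 15:7 split with *s* = 65%, an unadjusted preference reads (15 × 0.65 + 7 × 0.35)/22 = 12.2/22 = 55.5% instead of 50%. The unadjusted sign test then rejects 2.6% and Fisher's test 1.5%.

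**Additive score.** In simulation (20,000 runs, 11:11, standardised difference 0.626), a two-sample t test on the period differences keeps 80% power for period shifts of 0, 0.5, 1 and 2 SD. The loss is therefore specific to a better/worse answer.

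**The case against.** The strongest reply is that little remains once the valid parts of the design are credited. In a randomised cross-over with the observer blind to sequence, second versus first converts directly to one device versus the other. The protocol does not say that the answer is binary or that visit labels are shown, and display procedure is often left to a reading manual. The video reading names the OGS, so a score for each record may already be kept; the better/worse figures would then not apply to it. The graphical-report reading has no number in the outcome list, and outcomes 1 to 4 take their measures directly from the gait analysis. All of this stands, and it limits the point to a modest one. It does not remove the wording, which the protocol itself fixes in order-cued form for both readings.

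Three stronger readings are tempting and are not supported.

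- *A very large power loss at a mild tendency.* One could suppose that the observer disregards the record and answers that the later one is better in a share 2*s* − 1 of children, which is 30% at *s* = 65%. Power would then be 73/61/49/37% at 50/55/60/65%. But if the same share of answers is replaced in random direction, power is 73/61/48/35%. That loss comes from discarded records, not from order, and masking would recover it only if the order cue were what made the observer disregard them. Nothing in the protocol suggests this.
- *A false finding for one device.* At equal sequences there is none. At unequal sequences the bias arises only in an analysis that ignores period, and the protocol does not state that period will be ignored.
- *Failed blinding.* The stated masking of group and device is not contradicted. Only record order is left visible.

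**Conclusion.** The point holds as a low-priority improvement. Both readings are worded as the T2 record against the T1 record, and the stated blinding does not cover that order. If the answer is better/worse and the tendency is a shift, the cost after period adjustment is at most about 6 points of power for tendencies up to 65%. It reaches about 21 to 25 points only at a strong 80% tendency. These figures rest on an assumed 80% true preference, 11 children per sequence and a two-sided 5% Fisher test. The size of any real tendency is unknown and could be nil.

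The concern falls mainly on the graphical-report reading. The ankle-power outcome and the sample size of 22 are not touched. It is worth raising because the remedy is cheap and has to be in place before the records are read.

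**What to change.** In Outcome measures, replace the order-based rating rule in both observer paragraphs with a comparison of records coded A and B, with visit labels removed and the viewing order randomised across children. For the videos, show the T1 and T2 recordings separately and score each on the OGS on its own. For the graphical reports, ask how A compares with B. After reading, convert both results to Ankle-7 versus AFO within child, and analyse them with period in the model.

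A graded answer for the graphical reports is optional. With an assumed five-step scale, simulated power is about 95% even with no order tendency, so that gain is separate from viewing order.

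The cost is minor relabelling and file handling by someone other than the observers. The observers, recordings and visits stay the same.

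### Does listing the try-on of the second orthosis above the gait analysis in the first orthosis at T1 bias the device comparison?

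*Protocol*

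**What the plan says.** Proposed intervention describes a randomised two-sequence cross-over. One group uses the hinged AFO first and then Ankle-7, and the other group uses them in reverse. O_1 and O_2 denote the first and second device assigned, so each is AFO in one group and Ankle-7 in the other. Each device is worn for 4–6 weeks before it is assessed.

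- **T0, item 5:** a try-on of the "in-process first assignment orthoses (O_1) and subsequent delivery of them (see Annex A").
- **T1, heading:** "patients will receive the following procedures and assessments". Four numbered items follow.
- **T1, item 1:** a try-on of the "in-process second assignment orthoses (O_2").
- **T1, item 2:** "instrumental gait analysis and video recording of the walking while using O_1 (covered by elastic gaiters").
- **T1, items 3 and 4:** O_1 is withdrawn, then "delivery of O_2 to the patient".
- **T2, item 1:** "instrumental gait analysis and video recording of the walking while using O_2 (covered by elastic gaiters"). No try-on is listed.

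Under Outcome measures, blinded observers also give an "assessment of clinical improvement or worsening of the second situation compared to the first", from the videos and from the gait reports. Under Study population, the pilot phase has 5 children and the planned total is 22.

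**The concern.** Items 2 to 4 at T1 follow a natural order: measure in O_1, take it back, hand over O_2. It is therefore reasonable to read item 1 as also coming in its listed place. On that reading the child tries the competing device just before being measured in the device worn for the past weeks, and nothing comparable precedes the T2 measurement.

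The device tried on at T1 depends on the sequence: Ankle-7 in the AFO-first group, AFO in the Ankle-7-first group. If trying on one device disturbs gait differently from trying on the other, randomising the order does not remove the effect. Ankle push-off power, the first-listed outcome and the subject of the sample-size hypothesis, comes from these sessions, as do the blinded second-versus-first ratings. Measuring in O_1 before the try-on looks like a free remedy.

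**Working it through.** **The plan's own figure.** Study population gives N = 22 for 80% power and 5% type I error, with no effect size or SD, so 22 cannot be reproduced. It can only be inverted. For a paired comparison, two-sided 5% (sidedness is not stated):

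(1.960 + 0.842)/√22 = 2.802/4.690 = 0.597 SD of the within-child difference, or about 0.63 SD with the noncentral t. One-sided, the values are 0.53 and 0.55.

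This serves only as a yardstick below. N does not depend on the order of items at T1.

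**Model.** Let D be the true Ankle-7 minus AFO difference, π the ordinary period effect, e(Ankle-7) the effect on T1 gait of having tried on Ankle-7, and e(AFO) the same for AFO. The Ankle-7 minus AFO contrast within each sequence is:

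- AFO first: (Ankle-7 + π) − (AFO + e(Ankle-7)) = D + π − e(Ankle-7)
- Ankle-7 first: (Ankle-7 + e(AFO)) − (AFO + π) = D − π + e(AFO)

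The mean of the two is D + [e(AFO) − e(Ankle-7)]/2.

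**Same effect for both devices.** If e(AFO) = e(Ankle-7) = e, the bias is 0 at 11:11, and 0 at any split when the two sequence means are averaged (period adjustment). Only an unadjusted mean over unequal groups keeps a remainder, e × (n2 − n1)/(n1 + n2), where n1 is the AFO-first group. With an assumed e = 0.3 SD:

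- 12:10 split: 0.3 × (−2)/22 = −0.027
- 14:8 split: 0.3 × (−6)/22 = −0.082
- 3:2 split in the pilot: 0.3 × (−1)/5 = −0.06

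Any period effect leaves this remainder. It is not peculiar to the try-on.

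**Effect that differs by device.** Assumed values, in SD of the within-child difference:

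| e(Ankle-7) | e(AFO) | Bias in Ankle-7 minus AFO |
|---|---|---|
| 0.3 | 0 | (0 − 0.3)/2 = −0.15 |
| 0 | 0.3 | (0.3 − 0)/2 = +0.15 |
| 0.3 | 0.1 | (0.1 − 0.3)/2 = −0.10 |

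With 22 children and 20 df, a bias of 0.05, 0.10 or 0.15 SD would raise a two-sided 5% error rate to about 5.6%, 7.3% or 10.3%. To reach 0.15 SD from one device, the try-on must move gait by 0.3 SD. That is nearly half of the whole difference the trial appears sized to detect (0.3/0.63 = 0.48), and the other device's try-on must do nothing.

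**A special case.** Suppose the try-on pulls gait in O_1 a fraction c of the way toward the other device. Then e(Ankle-7) = cD and e(AFO) = −cD, and the bias is (−cD − cD)/2 = −cD. For positive c the difference shrinks, and when D = 0 the bias is 0, so no false superiority arises. A negative c would enlarge the difference. Nothing in the Protocol gives c a value or a sign.

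**Is the order a same-session sequence?** T0, T1 and T2 are introduced as phases of the project. T0 runs from taking measurements for tailor-made devices to fitting and delivering one of them, which can hardly be a single session. The wording at T0 item 5 places delivery after the try-on without saying how soon, and an in-process device is unfinished when tried. T1 may likewise extend over more than one day. The T1 heading does not prescribe an order.

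**The case for a change.** The best argument for a change is that the asymmetry is real as numbered and a later analysis plan cannot repair it, because an unmeasured device-specific effect cannot be separated from the device difference. The devices do differ by design: one is a hinged AFO, and the other has a carbon-fibre part meant to store and return energy. Different short-term effects are therefore conceivable. The T1 text gives neither the interval between try-on and measurement nor whether the child walks in the unfinished device. The pilot has an odd number of children ("5 children will be selected to meet the eligibility criteria for the study"), so its unadjusted mean could not be balanced.

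Some of this stands. A device-specific effect would bias the result by the formula above, and measuring first would set it to zero. The rest is weaker:

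- The gain is conjectural. The documents give no sign of an effect that would outlast a fitting and override 4–6 weeks of habituation.
- The remedy may cost something. Fitting O_2 early gives the workshop time to finish it before handover. Measuring first could mean an extra visit, or a longer gap between the O_1 measurement and delivery of O_2. The documents do not settle which.
- The fitting procedure is referred to Annex A at T0. That annex is not in the supplied text, so the interval and conduct of the try-on cannot be called absent from the plan.
- The pilot remainder belongs to period adjustment, which is commonly left to the SAP.
- A common effect would push the blinded ratings the same way in both groups. It drops out when the two sequences are contrasted.

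**Conclusion.** The plan can stand as written. The order of items at T1 would matter only if three conditions held together: the try-on and the O_1 measurement fall close together, the try-on changes gait measured after 4–6 weeks in another device, and the change differs between AFO and Ankle-7. The bias would then be [e(AFO) − e(Ankle-7)]/2, which is 0.15 SD in the assumed case of 0.3 SD from one device only. Otherwise the try-on is a period effect, and it contributes nothing with balanced sequences or period adjustment. The first condition is an inference from numbering, and the documents do not support the other two. What remains is a detail of scheduling: a team able to record gait in O_1 before the fitting, without an extra visit, loses nothing by doing so. The SD figures are illustrations built on assumed try-on effects. The yardstick of about 0.63 SD is back-solved from N = 22 under an assumed two-sided 5% test and is not stated in the Protocol.
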